| 
ENDPOINT(S)
 | 
Primary endpoint
 
Proportion of patients with individualized HbA1c target attainment per HEDIS criteria (<8% if age ≥ 65 years or with defined comorbidities listed in Appendix G or otherwise <7%) at 6 months without documented or severe symptomatic (BG ≤ 70 mg/dl) hypoglycemia at any time of day from baseline to 6 months.
 
The individual components of individualized HbA1c target attainment and absence of any documented symptomatic or severe hypoglycemia (BG ≤70 mg/dl) will also be evaluated as supportive analyses to evaluate consistency.
 
Secondary endpoint(s)
 
 ● Change in HbA1c from baseline (obtained at screening visit within one week of study initiation) to 6 months, ● Proportion of patients who remain on assigned basal insulin therapy (persistent with assigned therapy) at 6 and 12 months, ● Proportion of patients with individualized HbA1c target attainment per HEDIS criteria at 6 months without documented symptomatic (BG <54 mg/dl) or severe hypoglycemia at any time of day from baseline to 6 months, ● Proportion of patients with individualized HbA1c target attainment (per HEDIS criteria) at 12 months without documented symptomatic (BG ≤70 mg/dl) or severe hypoglycemia at any time of day from baseline to 12 months, ● Proportion of patients with individualized HbA1c target attainment per HEDIS criteria at 12 months without documented symptomatic (BG <54 mg/dl) or severe hypoglycemia at any time of day from baseline to 12 months. |

| | |
|----------------------------|--|

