9.2.3.1 Hypoglycemia classification

Hypoglycemia events will be categorized as follows:

- **Severe hypoglycemia:** Severe hypoglycemia is an event requiring 3rd party assistance of another person to actively administer carbohydrate, glucagon, or other resuscitative actions. These episodes may be associated with sufficient neuroglycopenia to induce seizure, unconsciousness or coma. Plasma glucose measurements may not be available during such an event, but neurological recovery attributable to the restoration of plasma glucose to normal is considered sufficient evidence that the event was induced by a low plasma glucose concentration. The definition of severe symptomatic hypoglycemia includes all episodes in which neurological impairment was severe enough to prevent self-treatment and which were thus thought to place patients at risk for injury to themselves or others. Note that “requires 3rd party assistance” means that the patient could not help himself or herself. Assisting a patient out of kindness, when assistance is not required, should not be considered a “requires assistance” incident.
- **Severe hypoglycemia** will be qualified as an SAE only if it fulfills SAE criteria. All events of seizure, unconsciousness or coma must be reported as SAEs.
- **Documented symptomatic hypoglycemia:** Documented symptomatic hypoglycemia is an event during which typical symptoms of hypoglycemia accompanied by a measured plasma glucose concentration of ≤ 70 mg/dL (3.9 mmol/L). Clinical symptoms that are considered to result from a hypoglycemic episode are, eg, increased sweating, nervousness, asthenia/weakness, tremor, dizziness, increased appetite, palpitations, headache, sleep disorder, confusion, seizures, unconsciousness, or coma.
- **Asymptomatic hypoglycemia:** Asymptomatic hypoglycemia is an event not accompanied by typical symptoms of hypoglycemia but with a measured plasma glucose concentration less than or equal to 70 mg/dL (3.9 mmol/L).
- **Probable symptomatic hypoglycemia:** Probable symptomatic hypoglycemia is an event during which symptoms of hypoglycemia are not accompanied by a plasma glucose determination, but was presumably caused by a plasma glucose concentration less than or equal to 70 mg/dL (3.9 mmol/L); symptoms treated with oral carbohydrate without a test of plasma glucose.

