Patients will be instructed to measure finger stick plasma glucose levels prior to the administration of carbohydrates whenever symptomatic hypoglycemia is suspected, unless safety considerations necessitate immediate glucose rescue prior to confirmation, and then a glucose measurement should be performed as soon as safe, with appropriate diary documentation. Details on hypoglycemia episodes will be captured in the patient e-diaries and then available in the vendor web based portal. Patients will contact the sites as soon as possible following severe events to review the details and decide on any necessary measures to be taken.

Symptomatic hypoglycemia episodes will be documented on the Low Blood Glucose Event (LBGE) page in the clinical data base. Symptomatic hypoglycemia events fulfilling the criteria of a SAE will also be documented on AE and SAE forms form in the e-CRF.

For discussion of endpoints related to hypoglycemia, see [Section 9.2.3.1](#)

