1.3 DETERMINATION OF SAMPLE SIZE

1.3.1 Original sample size

At time of initial protocol, calculations to determine the sample size of 1635 patients per treatment group are based on superiority testing of the primary efficacy variable of the proportion of patients reaching individualized HbA1c target at Month 6 without a documented symptomatic (BG \leq 70 mg/dL) or severe hypoglycemic event at any time of day from baseline to Month 6, with the following assumptions:

- Individualized HbA1c target attainment per HEDIS criteria of $<8\%$ if older or presence of medical comorbidities, or otherwise $<7\%$,
- An absolute difference of 5.5% in favor of Toujeo in patients assigned a target HbA1c $<7\%$, assuming a 30.1% rate in the Toujeo arm, based on data from the EDITION 3 study,
- An absolute difference of 5.4% in favor of Toujeo in patients assigned a target HbA1c $<8\%$, assuming a 55.8% rate in the Toujeo arm, based on data from the EDITION 3 study,
- An absolute overall (weighted average) difference of 5.5% in favor of Toujeo for all patients combined, assuming that 70% of the study patients would have a target HbA1c $<7\%$, and 30% would have a target HbA1c $<8\%$, based on data from a commercially available database,
- A maximum overall response rate of 33% in the comparator basal insulins arm,
- A 2-sided chi-squared test at the 5% significance level, with 90% power,
- All patients will be eligible for the primary endpoint analysis.

The assumptions are based on data from the EDITION program.

As a logistic regression model will be used for the primary analysis of the composite endpoint of individualized HbA1c target attainment without hypoglycemia, it is anticipated that the power will be higher due to reduced estimate variability compared with the chi-square test. Calculations were made using nQuery Advisor 6.01.

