2.4.4.1 Analysis of primary efficacy endpoint

The primary efficacy analysis will be performed on the ITT population, using all post-baseline HbA1c data available and hypoglycemia events collected on the 6-month randomized period, regardless of IMP discontinuation.

The primary efficacy endpoint: proportion of patients reaching individualized HbA1c target at 6 months without documented symptomatic ($BG \leq 70$ mg/dL) hypoglycemia will be analyzed using a logistic regression model, adjusting for HbA1c target and other stratification factors used at randomization: SU use (y/n), GLP-1 RA use (y/n) and baseline HbA1c (as continuous). a superiority test will be performed to compare this proportion between treatment groups at IA

(2-sided, alpha = 0.010) and at final 6-month analysis (2-sided, alpha = 0.046). Treatment difference will be assessed by odds ratios and CIs. For the primary efficacy analysis, the randomization strata from IVRS will be used.

Patients with missing HbA1c data at 6 months will be regarded as not having reached HbA1c target. In order to examine the consistency of this analysis, the individual components of HbA1c target attainment and absence of any documented symptomatic (BG ≤70 mg/dL) or severe hypoglycemia will also be evaluated. Each individual component (HbA1c target attainment at 6 month, or absence of any documented symptomatic [BG ≤70 mg/dL] or severe hypoglycemia), will be compared between treatment groups, respectively, using same logistic regression model as the primary efficacy analysis.

Sensitivity analyses

The sensitivity analyses of primary efficacy endpoint will be performed at time of 6-month database lock.

- **On-treatment sensitivity analysis.**

A sensitivity analysis for the primary efficacy endpoint will be performed on the 6-month on-treatment period, as defined in [Section 2.1.3](#).

- **Multivariate analysis.**

As a sensitivity analysis, a multivariate analysis will be performed, adding the following baseline covariates in the model: BMI, duration of diabetes, baseline PAM score, hypoglycemic history and age. a backward selection procedure at 0.10 level will be used get the final model with these exploratory factors. Treatment effect will be re-evaluated based on the final model.

Country (USA/Canada) and US region effect systematic group difference will be explored.

- **Sensitivity analysis of primary efficacy endpoint with randomization strata from e-CRF.**

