For documented hypoglycemia, if a patient drops out from the study prior to 6 months and no documented hypoglycemia is entered into the CRF during the first 6-month treatment period, the patient status with regard to documented hypoglycemia (presence or absence of hypoglycemia) will be considered as missing. Similarly, if a patient drops out from the study prior to 12 months and no documented hypoglycemia is entered during the 12-month treatment period, the patient's documented hypoglycemia status will be considered missing. If a patient has a documented hypoglycemia event within the time frame, then this subject will be considered as a subject with documented hypoglycemia, no matter it is a completer or early withdrawal.

Missing data will be imputed 100 times to generate 100 complete data sets with the MI with Markov Chain Monte Carlo (MCMC) method in SAS procedure in two steps.

- Step 1: Six-month HbA1c value will be imputed using the regression method with stratification factors and treatment. For each simulation leading to imputed HbA1c values outside of 3.5% to 16%, another value will be redrawn for imputation.
- Step 2: If the 6-month documented (BG \leq 70 mg/dL) hypoglycemia status is missing, after Step 1, HbA1c is imputed, 6-month documented (BG \leq 70 mg/dL) hypoglycemia status will be subsequently imputed using a logistic regression method with 6-month HbA1c, stratification factors, and treatment.

For each of the 100 imputed datasets, the composite endpoint will be constructed and compared between treatment groups using the same logistic regression model as specified above in the primary efficacy endpoint analysis. The estimates from the 100 fitted models will be combined to provide an overall estimate with corresponding confidence intervals (CI). The difference between treatments and the corresponding CI will be presented. The imputed values of HbA1c will also be used in the analysis of HbA1c change as continuous variable (secondary efficacy endpoint).

- **Sensitivity analysis of primary efficacy endpoint with tipping point analysis.**

Robustness of the primary analysis results to departure from the MAR assumption will be explored in the ITT population using tipping-point analysis based on the pattern mixture model approach.

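### The SAP sentence specifying the primary test omits severe hypoglycemia, so it conflicts with the SAP's own composite definition for severe events not captured as documented symptomatic events

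*SAP*

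**What the plan says.** **Where severe events are part of the composite.** The SAP includes them in its endpoint definition (2.1.3.1), its sample-size basis (1.3.1), the component analysis within 2.4.4.1 and the outcome for the SIDES subgroup search, which it calls the primary endpoint. Protocol 9.1 (endpoint) and 11.4.2.1 (primary analysis) include them too.

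**Where they are absent.**
- The sentence in SAP 2.4.4.1 that sets out the logistic model, tested at 0.010 at the interim and 0.046 at the final 6-month analysis, gives the endpoint as the "proportion of patients reaching individualized HbA1c target at 6 months without documented symptomatic" (BG ≤70 mg/dL) hypoglycemia. Severe events are not mentioned.
- The multiple-imputation analysis opens by saying that it handles documented or severe hypoglycemia. Its operative rules then use documented status only: "If a patient has a documented hypoglycemia event within the time frame, then this subject will be considered as a subject with documented hypoglycemia". Step 2 also imputes only documented (BG ≤70 mg/dL) status. The tipping-point analysis reuses this method.

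**Related rules.**
- SAP 2.5.2 treats a symptomatic event with no glucose value as documented, and so as a composite failure. It also fails anyone who ends the study within the 6-month randomized period.
- For severe events, protocol 9.2.3.1 says "Plasma glucose measurements may not be available during such an event" and accepts neurological recovery as evidence.
- Protocol 10.6.1 asks for a reading before carbohydrate "unless safety considerations necessitate immediate glucose rescue prior to confirmation, and then a glucose measurement should be performed as soon as safe".
- The primary-endpoint row of the protocol synopsis reads "without documented or severe symptomatic" and then gives the ≤70 mg/dL cut-off. This attaches the cut-off to severe events, whereas protocol 9.1 attaches it only to documented symptomatic events.

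SAP 1.5 lists the changes from the protocol's statistical section and does not list this one. SAP 1.6 reports no modifications.

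**The concern.** The sentence that omits severe events is the one a programmer would use to build the variable for the only confirmatory test. If it is followed as written, the tested composite differs from the defined one and from the component analysis meant to support it. The missing-glucose rule in SAP 2.5.2 does not fully close the gap. It covers a glucose value that is absent, not one that is present but above 70 mg/dL, and protocol 10.6.1 makes such a reading foreseeable after rescue.

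The trial is open-label and has an interim efficacy look. Two written versions of the primary endpoint leave a choice that would appear data-driven if it were made after results are known.

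**Working it through.** **1. How each severe event is classified.** Take a patient at HbA1c target whose only event is severe.

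| Event as recorded | SAP 2.1.3.1 | SAP 2.4.4.1 read literally, with 2.5.2 |
|---|---|---|
| Symptoms recorded, glucose ≤70 mg/dL | failure | failure |
| Symptoms recorded, glucose missing | failure | failure (2.5.2) |
| Recorded glucose above 70 mg/dL | failure | **success** |
| Symptoms not recorded | failure | **success** |
| Any of these, study ended before Month 6 | failure | failure (2.5.2) |

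The two readings differ only in the third and fourth rows. In the imputation analyses, a dropout with an event of those two kinds and no other has no documented event, so the status rule classes that patient as missing and Step 2 may impute absence.

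**2. The plan's own figures.** The inputs from SAP 1.3.1 are "A 2-sided chi-squared test at the 5% significance level, with 90% power", "A maximum overall response rate of 33% in the comparator basal insulins arm" and "An absolute overall (weighted average) difference of 5.5% in favor of Toujeo for all patients combined". So p₁ = 0.33, p₂ = 0.385, Δ = 0.055 and p̄ = 0.3575.

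- n = [1.960·√(2p̄(1−p̄)) + 1.282·√(p₁(1−p₁)+p₂(1−p₂))]² / Δ² = (1.960 × 0.6778 + 1.282 × 0.6767)² / 0.003025, which gives 1594 per arm.
- With continuity correction, (n/4)·[1+√(1+4/(nΔ))]² = 1630 per arm.
- With the unrounded weighted rates (Toujeo 0.7 × 30.1 + 0.3 × 55.8 = 37.81%; comparator 0.7 × 24.6 + 0.3 × 50.4 = 32.34%), the corrected figure is 1634, against the stated 1635.

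The sample-size text already describes the composite with severe events. Restoring them in the test sentence therefore leaves 1635, and then 1662 after the interim was added, unchanged.

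**3. Size of the effect.** The documents give no severe-event rate. Let *s* be the assumed share of randomized patients who are at target and whose only event falls in the third or fourth row. The number moved is 1662·*s* per arm. Power at the final look, taken as a fixed-sample test at 0.046, is Φ{[Δ√1662 − 1.995·√(2p̄(1−p̄))] / √(p₁(1−p₁)+p₂(1−p₂))}. The planned rates are taken as the literal count, and *s* is then moved to failure.

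| *s* comparator / Toujeo | Patients moved per arm | Power |
|---|---|---|
| 0 / 0 | 0 / 0 | 0.906 |
| 0.2% / 0.2% | 3 / 3 | 0.906 |
| 0.5% / 0.5% | 8 / 8 | 0.908 |
| 1.0% / 1.0% | 17 / 17 | 0.909 |
| 0 / 0.5% | 0 / 8 | 0.846 |
| 0.5% / 0 | 8 / 0 | 0.948 |

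For scale, the null standard error of the difference at 1662 per arm is √(2 × 0.3575 × 0.6425/1662) = 0.0166. The final threshold is 1.995 × 0.0166, or about 3.3 points. An imbalance of 8 patients moves the difference by 0.5 points. The top value is generous: *s* = 1.0% would need, for instance, 2% of patients with a severe event and half of those in the third or fourth row with no other qualifying event (2% × 50%), with every one of them at target.

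**The case against.** The strongest reply is that the SAP has not redefined anything. The sentence in 2.4.4.1 refers to a term already defined in 2.1.3.1. It also drops the time-of-day and observation-period wording, so it reads as shorthand. The component analysis beside it, the SIDES outcome and the protocol's primary analysis all keep severe events, and SAP 1.5 declares no change. That stands. The misclassification follows only if the one sentence is programmed as written, and a programmer working from 2.1.3.1 would get it right. It does not remove the need for an edit, because the sentence attached to the test should not need correcting from elsewhere.

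A reader might infer that any severe event without a reading of 70 mg/dL or below becomes a success. The documents do not support that: SAP 2.5.2 fails symptomatic events with missing glucose, and protocol 10.6.1 names severe events as severe symptomatic.

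A reader might also infer that the imputation rule can create primary-endpoint successes. It cannot. It belongs to sensitivity analyses, and in the primary analysis early study end is already failure. Even there, the SAP says the composite is constructed in each imputed dataset. If that construction uses 2.1.3.1, an observed severe event would still count as failure. The text is incomplete rather than plainly wrong, which is why the conclusion is *could be imputed event-free*.

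SAP Figure 2 (classification with missing items) and SAP Appendix A are not visible in the public copy. How they would classify a severe event with a higher reading could not be checked, and nothing here relies on them.

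**Conclusion.** The inconsistency is real and lies in the specification of the confirmatory test. Its reach is narrow: severe events with a recorded glucose above 70 mg/dL, or without symptoms recorded, in patients who reach target and have no other qualifying event. The imputation gap concerns the same kind of event, in the MAR and tipping-point analyses only.

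The number affected is probably small. Under the assumed 0.2% to 1.0% per arm, 3 to 17 of 1662 patients change status, and power stays at about 0.91 if the arms are affected equally. The shifts to 0.846 or 0.948 need all the affected patients to be in one arm, for which the documents give no basis, so the direction is unknown. It would be wrong to conclude that the SAP has removed severe hypoglycemia from its primary endpoint or that the trial's power is compromised. The case for acting is that one operative sentence contradicts the definition and can be settled before any unblinded result exists.

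**What to change.** Before the interim database lock:

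1. In the primary-analysis sentence of SAP 2.4.4.1, add *or severe* so that it matches 2.1.3.1 and protocol 11.4.2.1.
2. In the multiple-imputation text of 2.4.4.1, define the missing-status rule, the rule for patients with an observed event and Step 2 on documented symptomatic (BG ≤70 mg/dL) or severe hypoglycemia. The tipping-point analysis then inherits the correction.
3. State once, in 2.1.3.1 or 2.5.2, that any event classified as severe is a composite failure whatever its glucose value, when the reading was taken, or whether symptoms were recorded.
4. Align the primary-endpoint wording in the protocol synopsis with protocol 9.1, so that the ≤70 mg/dL cut-off applies only to documented symptomatic events.

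The cost is wording in the SAP and synopsis, plus a check of the endpoint programming. No new data, visits or patients are needed, and N stays at 1662 per arm.

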| | 
patient-level randomization. Given the potential impact of certain variables on the primary endpoint, randomization will be stratified by individualized HbA1c target (<8%/<7%), SU use ever (y/n), GLP-1 RA use ever (y/n) and baseline HbA1c (<9%/≥9%).
 
The two treatment arms of the study will be:
 
 1) Toujeo with its available patient support program, 2) Commercially available insulin detemir (Levemir®) or insulin glargine-U100 (Lantus®) with or without a patient support program. 
Randomization will be 1:1 between the two arms of the study and the choice of comparator basal insulin will be based on the usual practice at the clinical site and not by randomization.
 
The study will include a 6 month treatment period ending in assessment of the primary and secondary endpoints followed by a 6 month extension period for assessment of certain additional endpoints. It will also include an interim analysis (IA) for overwhelming efficacy on the primary endpoint, planned to be conducted when approximately 1800 patients have been randomized and completed their 6-month visit. If the targeted sample size (1800) cannot be reached, it could be considered to include a lower number of patients, however not below 1700. In this case, the nominal significance level to be spent at interim and at final 6-month analyses would be recalculated accordingly before the database lock for IA.
 
An independent Data Monitoring Committee (DMC) will review data from this IA.
 
Dose regimen: Patients will be initiated on basal insulin therapy per the prescribing instructions for each insulin and titrated to a target fasting glucose consistent with the individualized HbA1c target according to the typical protocol used at each site and investigator discretion.
 
Financial support will be provided by Sanofi for the cost of commercially available basal insulin as well as for Toujeo.
 
Collection of hypoglycemia events and symptoms:
 
A glucometer with wireless data transmission capabilities will be used to collect self-measured plasma glucose (SMPG) including SMPG associated with hypoglycemic symptoms. An electronic diary (eDiary) will be used to record the symptoms of hypoglycemia and other relevant clinical information.
 |

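### The MAR imputation gives study dropouts with no recorded hypoglycemia a full 6-month risk, which biases imputed hypoglycemia upward in the multiple-imputation and tipping-point sensitivity analyses

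*SAP*

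**What the plan says.** SAP 2.4.4.1 plans a multiple imputation under MAR to assess the impact of missing data. It treats study dropouts in two ways:

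- **No event recorded.** Where "if a patient drops out from the study prior to 6 months and no documented hypoglycemia is entered into the CRF" in the 6-month period, the hypoglycemia status is set to missing.
- **Event recorded.** "If a patient has a documented hypoglycemia event within the time frame, then this subject will be considered as a subject with documented hypoglycemia", whether the patient completed or withdrew.

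Step 1 imputes 6-month HbA1c. In Step 2 the missing "hypoglycemia status will be subsequently imputed using a logistic regression method with 6-month HbA1c, stratification factors, and treatment". No other predictor is listed for Month 6; dropout day and time already observed without an event do not appear. The Month 12 status is coded in the same way.

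The tipping-point analysis (same section) reuses this imputation. Its penalty δ is added to imputed HbA1c only, and δ = 0 is taken to represent MAR.

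The primary analysis works differently. Missing 6-month HbA1c counts as not reaching target (SAP 2.4.4.1), and premature end of study counts as failure on the composite (SAP 2.5.2).

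**The concern.** Whether a dropout's status is known depends on the status itself: an event before leaving makes it known, no event makes it missing. Given the covariates in the Step 2 model, missingness therefore depends on the outcome, although the analysis is labelled MAR. Two errors follow, both upward:

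1. The model is fitted to patients with known status, that is, completers plus only those dropouts who had events. The fitted risk is too high.
2. Observed event-free time is discarded. A patient who left event-free on Day 170 gets the same 6-month risk as one who left on Day 5.

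The stake is the value of this analysis as a check. Counting dropouts as failures, as the primary analysis does, favours the arm with fewer dropouts. An imputation that overstates hypoglycemia in dropouts errs in the same direction, so it cannot remove that artefact completely. In the tipping-point runs the reference point δ = 0 carries the same error. Since δ reaches hypoglycemia only indirectly, through HbA1c as a predictor, no value of δ corrects the hypoglycemia step itself.

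**Working it through.** **Design figures.** The plan states no figure for imputed hypoglycemia, so there is none to reproduce. To scale the result I use the design rates in SAP 1.3.1: "A maximum overall response rate of 33% in the comparator basal insulins arm" and "An absolute overall (weighted average) difference of 5.5% in favor of Toujeo for all patients combined", that is 33% against 38.5%. With "A 2-sided chi-squared test at the 5% significance level, with 90% power", the usual formula gives

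n = [1.960·√(2·0.3575·0.6425) + 1.282·√(0.33·0.67 + 0.385·0.615)]² / 0.055² = 1594 per arm, or 1630 with continuity correction.

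Both are within 3% of the stated 1635.

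**Assumptions (not in the documents).** 6-month risk R, fraction q leaving the study, dropout time u as a fraction of the 6 months, dropout independent of event time. The worked case has R = 0.30, q = 0.10, u uniform and a constant hazard h = −ln(0.70) = 0.3567.

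**Worked case.**

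- Event before dropout, among dropouts: e = 1 − R/h = 1 − 0.30/0.3567 = 0.159.
- Risk fitted by the SAP rule: (0.90·0.30 + 0.10·0.159)/(0.90 + 0.10·0.159) = 0.2859/0.9159 = 0.312.
- Correct remaining risk in event-free dropouts: (0.30 − 0.159)/(1 − 0.159) = 0.168.
- Ratio: 0.312/0.168 = 1.86.
- Hypoglycemia in all dropouts after imputation: 0.159 + 0.841·0.312 = 0.421, against 0.30.
- Whole arm: 0.90·0.30 + 0.10·0.421 = 0.312, a rise of 1.2 points.

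**Dependence on timing.** Simulation with 2 million patients per scenario, constant hazard:

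| Dropout timing | Imputed vs correct (R = 30%, q = 10%) | Ratio | Ratio over R 10–50%, q 5–20% |
|---|---|---|---|
| Early, Beta(1,3) | 30.6% vs 23.5% | 1.30 | 1.22–1.40 |
| Uniform | 31.2% vs 16.7% | 1.86 | 1.65–2.17 |
| Late, Beta(3,1) | 31.7% vs 8.8% | 3.60 | 3.04–4.34 |

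With uniform dropout, q = 10% and R 20–40%, a falling hazard (Weibull shape 0.6) gives ratios up to 2.60 and a rising one (shape 2) down to 1.38. Over the constant-hazard grid, arm-level incidence rises by 0.1 to 4.6 points.

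**Effect on the treatment difference.** If HbA1c attainment A is independent of hypoglycemia, composite response is A(1 − R), and the arm loses A times its excess incidence. With R = 0.30 in both arms, A = 0.385/0.70 = 0.550 for Toujeo and 0.33/0.70 = 0.471 for the comparator. The excess is 1.21 points at 10% dropout and 2.67 at 20% (uniform).

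- Equal 10%: 0.550·1.21 − 0.471·1.21 = 0.67 − 0.57 = 0.1 point. The largest shift found with equal dropout is 0.28 (R = 0.40, 20% in both arms).
- Toujeo 10%, comparator 20%: 0.471·2.67 − 0.550·1.21 = 1.26 − 0.67 = 0.6 point toward Toujeo.
- Toujeo 20%, comparator 10%: 0.550·2.67 − 0.471·1.21 = 1.47 − 0.57 = 0.9 point against Toujeo.
- At R = 0.40 the two unequal cases give 0.8 and 1.2 points; at R = 0.20, 0.4 and 0.6.

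For scale, the standard error of the difference at 1662 per arm is √[(0.33·0.67 + 0.385·0.615)/1662] = 1.7 points.

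**The case against.** The strongest reply is that the effect is small where it matters. It touches sensitivity analyses only. Patients who stop study insulin are asked to keep reporting hypoglycemia and to return at Day 180 (Protocol 10.3.3), so only those who leave the study are concerned. The imputation also still does most of its job. In a simulated null with 15% versus 25% dropout and 30% risk, counting dropouts as failures gives a spurious 2.9 points, while the SAP imputation leaves 0.7 with uniform dropout, 0.3 with early and 0.95 with late dropout. About two thirds to nearly 90% of the artefact is removed. All of this stands and limits the point.

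It can also be said that setting these patients to missing is defensible. The trigger is that no event was entered, which is not the same as verified event-free follow-up. Sites enter events at visits (Protocol 9.2.2.2.3), no trial visit falls between Day 1 and Day 180 (Protocol 1.2), the Day 45 and Day 90 reviews are encouraged (Protocol 10.1.1.6), and the assessment at withdrawal is done if possible (Protocol 10.3.5). Treating every day up to dropout as event-free could understate hypoglycemia. This stands too and shapes the fix, but it does not justify a full-period risk for everyone.

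A reader might also infer that an observed severe event could be overwritten, because Step 2 names only documented hypoglycemia. The documents do not support that. The same section says that documented or severe hypoglycemia is handled in the imputation, and the composite built afterwards includes severe events (SAP 2.1.3.1), so an observed severe event fails it whatever status is drawn.

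**Conclusion.** The coding and the Step 2 model bias imputed hypoglycemia upward in event-free study dropouts, even when dropout is unrelated to outcome, and the tipping-point analysis inherits the bias. The direction follows from the SAP text alone; the size does not.

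Under a constant hazard the overstatement among the imputed patients runs from about 1.2-fold (early dropout) to 4.3-fold (late dropout). A reader might infer that imputed hypoglycemia is nearly doubled. That fits only dropout spread evenly with a roughly constant hazard, and only the event-free dropouts; at arm level the same case is 31.2% instead of 30.0%.

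Nor do the documents support the inference that the treatment comparison is materially biased as it stands. With equal dropout the difference moves by at most about 0.3 of 5.5 points. It takes unequal dropout, such as 10% versus 20%, to move it by roughly 0.5 to 1.2 points (risks of about 30% to 40%; somewhat less at 20%), and the direction depends on which arm loses more patients. Such an imbalance is possible in an open-label trial whose support program differs by arm, but the documents do not state one. The primary analysis does not use this imputation. The change is worth making because the rule is wrong by construction and cheap to correct.

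**What to change.** In Step 2, impute only the unobserved remainder of the period, conditional on no event up to day u. Define u as the last date with confirmed hypoglycemia data: the last site review or meter or e-diary transmission, otherwise the last contact. Either of two models will do:

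- a time-to-first-event model (piecewise exponential, or complementary log-log with a log follow-up offset) with HbA1c, strata and treatment; or
- an event drawn with probability 1 − (1 − p)^((180 − u)/180), with p estimated from patients with complete follow-up. At p = 0.30 this gives 29% for u = 5 and 2% for u = 170, where the present rule gives both patients the same risk.

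Use the same rule at Month 12 and in every tipping-point run.

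The cost is SAP wording and a little code. There are two downsides. A hazard shape must be assumed, and it can be varied. Events before dropout may be under-recorded, so the current rule should be kept alongside as a conservative bound.
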